10.1.3 Follow up of (Serious) Adverse Events

If adverse events occur, patients are followed-up with extra-visits after 14 days until the issue has resolved. This applies to patients who continue with the study but also to patients who prematurely exit the study. In case subjects are lost to followed-up, study personnel will contact the treating psychiatrists (or if unavailable, the general practitioners) in order to inform on serious adverse events and the recommendations for follow-up clinical examinations. In cases of headaches for example, care would include the prescription of a non-steroidal antirheumatic drug, i.e. pain medicine, according to the person's preferences, medical history, or interaction with existing medication.

11. STATISTICAL METHODS

A two-tailed p-value of $< .05$ is considered to be statistically significant in all analyses. We will also report effect sizes for the comparisons of primary and clinical secondary outcome variables between groups.

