11.1 Hypotheses

Aim 1: investigate the clinical and functional neural changes following 15 sessions of daily rTMS

Hypothesis 1a (main hypothesis): lf-rTMS (inhibitory) will be superior over placebo or iTBS (facilitatory) in all clinical and motor behavioral measures, e.g. greater reduction in SRRS scores from baseline, greater increase in activity levels, or coin rotations.

Hypothesis 1b: lf-rTMS will reduce aberrant functional connectivity in the motor system, e.g. between thalamus and M1. lf-rTMS will alter regional CBF in the motor system and increase SMA and M1 activity during the fMRI task. No relevant changes are expected in the sham group, iTBS may deteriorate neural alterations.

Hypothesis 1c: cortical excitability will be differentially changed with rTMS. Lf-rTMS will increase SIC1, while iTBS will reduce SIC1.

Aim 2: characterization of psychomotor slowing (PS) in schizophrenia spectrum disorders compared to healthy controls

Hypothesis 2a: Patients will have poorer performance on all motor tasks, eg. reduced activity levels, increased postural sway, and less coin rotations

Hypothesis 2b: Patients will have aberrant structural and functional connectivity within the motor system, as well as increased CBF in basal ganglia and decreased CBF in premotor/motor cortex. Applying network metrics, the functional motor network will be less efficient in schizophrenia.

Hypothesis 2c: Behavioral measures of PS will be associated with aberrant motor network structure, perfusion, function, and connectivity. For example, patients with strong PS will have increased resting state functional connectivity between thalamus and M1. PS severity will be linked to reduced structural motor network efficiency, lower M1 and SMA activity during the fMRI task, and increased SMA perfusion at rest.

Hypothesis 2d: Patients will have increased motor cortex excitability (e.g. reduced SICI), which will be linked to measures of PS.

Aim 3 characterize short term dynamics of PS

Hypothesis 3a: in very few subjects we expect relevant spontaneous improvements in PS measures. The majority will have less than 20% fluctuation of motor parameters within 3 weeks

Hypothesis 3b: we expect slight longitudinal changes in resting state functional connectivity and perfusion of the motor system, but no structural changes.

Aim 4: to describe the short-term and medium-term clinical outcome of 3 weeks of rTMS intervention

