11.2 Determination of Sample Size

The main effects of the 3-week interventions on PS (SRRS scores) will be calculated in a repeated measures design including 2 measures (Baseline, week 3) and four groups (If-rTMS, iTBS, sham, waiting group-If-rTMS). Assuming a moderate effect size ($f = 0.23$) as indicated by our pilot data in a repeated measures ANOVA with moderate correlation between time points (0.5), a power of 0.95 and an $\alpha = 0.05$, we would need 88 patients (22 per group).

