11.4.2 Primary Analysis

The primary analysis will be a repeated measures ANOVA of SRRS scores with two timepoints (within

subjects: baseline and week 3) and four groups (lf-rTMS, iTBS, sham, waiting group-If-rTMS). In case of significant baseline demographic or clinical group differences, we will adjust for these in an repeated measures ANCOVA of SRRS.

The analysis will be performed by the PI and his team in SPSS using data from the RedCap database.

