11.4.3 Secondary Analyses

Secondary analyses focus on the secondary outcomes (see 5.2) and hypotheses (see 11.1).

Crosstabs are used to calculate the proportion of responders ($\geq 30\%$ reduction in SRRS from baseline) across groups. Repeated measures ANOVAs will clarify the time-course of SRRS change from baseline to week 6 (including week 1, 2, 3 and 6) and differences between groups.

Repeated measures ANOVAs will test the change of clinical and motor rating scales between baseline and week 3, week 6, and week 24 and differences between groups.

Linear regression analyses will test the association between neuroimaging markers (resting state perfusion, connectivity, fMRI activation, ect.) and measures of PS at baseline.

Repeated measures ANOVAs will test the longitudinal changes in neuroimaging markers from baseline to week 3.

All analyses will be performed by the PI and his team or collaborators with permission of the PI.

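### The .05 threshold applies to every analysis and no multiplicity control is stated, so some false positive secondary and imaging results are likely; the primary SRRS test is not affected

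*Combined protocol and SAP*

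**What the plan says.** Section 11 sets one threshold for the whole trial: a two-tailed p-value below .05 "is considered to be statistically significant in all analyses". It also promises effect sizes for the primary and clinical secondary comparisons.

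Section 11.4.2 names a single primary test: "The primary analysis will be a repeated measures ANOVA of SRRS scores with two timepoints" and four groups.

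The hypotheses are much wider. Hypothesis 1a, labelled the main hypothesis in section 11.1, states that "lf-rTMS (inhibitory) will be superior over placebo or iTBS (facilitatory) in all clinical and motor behavioral measures". Hypotheses 1b and 1c cover connectivity, perfusion, task activation and excitability. Hypotheses 2a-2d cover patient-control differences and links between slowing and brain measures. Hypotheses 4a and 4b cover later clinical and functional outcome.

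Section 11.4.3 plans repeated measures ANOVAs for the scales and imaging markers, crosstabs for responders, and an open-ended set of regressions: "Linear regression analyses will test the association between neuroimaging markers (resting state perfusion, connectivity, fMRI activation, ect".

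Only hypothesis 4c (section 11.1) and the aim on imaging markers of response (section 4.1) are called exploratory. Neither section 11 nor the imaging methods in section 9.2.2.4 mentions a family, gatekeeping, FDR, or a voxel, cluster or region-of-interest correction.

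**The concern.** The plan does more than leave multiplicity unmentioned: it gives a decision rule and says that the rule covers everything. Followed as written, any secondary or imaging test with p below .05 counts as significant and can be cited for a directional hypothesis. No rule says how many measures, or which comparator, must succeed before hypothesis 1a is supported.

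The stake is mainly mechanistic. Section 3.1.8 presents the trial as allowing causal inference on the pathobiology of slowing, and section 3.7 says that its results will be used to plan further trials. Those mechanistic conclusions rest on the imaging and excitability tests, for which no error control is stated.

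**Working it through.** **The plan's own figure.** Section 11.2 gives f = 0.23, correlation 0.5, alpha 0.05, power 0.95 and 88 patients (22 per group). For the group-by-time interaction with 4 groups and 2 time points:

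- Noncentrality = f² × N × 2 / (1 − 0.5) = 0.0529 × 88 × 2 / 0.5 = 18.6, with 3 and 84 degrees of freedom.
- Power is 0.957. The smallest N reaching 0.95 is 86, or 88 with equal groups.

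The stated N reproduces. It is sized for one test at .05. The plan gives no number of tests and no family-wise error rate, so these must be built up from the outcome lists.

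**Counting non-imaging tests**, one between-group test per measure:

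| Source | Tests |
|---|---|
| Responders at weeks 1, 2, 3, 6, 24 (5.2.1) | 5 |
| SRRS time course (11.4.3) | 1 |
| UPDRS, BFCRS, AIMS, PANSS, BNSS, IPAQ, SNS (5.2.1, instruments in section 9) | 7 |
| Actigraphy, coin rotation (5.2.2) | 2 |
| SICI, ICF, MEP (5.2.3) | 3 |
| Sway, eyes open and closed (5.2.3) | 2 |
| **Subtotal** | **20** |
| Excitability as measured in 9.2.2.3 (SICI at two intervals, ICF at two, RMT, MEP: 6 instead of 3) | +3 |
| GAF, SOFAS, UPSA-brief (5.3, listed as other outcomes) | +3 |
| **Total** | **26** |

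**False positives if all nulls are true.**

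- Expected number: 0.05 × 20 = 1.0; 0.05 × 26 = 1.3. Correlation does not change this.
- At least one, independent tests: 1 − 0.95^20 = 0.64; 1 − 0.95^26 = 0.74.
- At least one of 26, treated as two-sided z tests with a common correlation: 0.62 at 0.3 and about 0.48 at 0.5 (numerical integration over the shared component).

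**Imaging.** Section 5.2.4 lists three domains but no number of regions or connections. As an illustration only, assume 7 unilateral motor regions with all pairs tested: 7 × 6 / 2 = 21 connections, 0.05 × 21 = 1.05 expected, and 1 − 0.95^21 = 0.66 under independence. Perfusion, task activation and the baseline regressions would come on top.

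**The case against.** The strongest points on the other side are these.

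- **The threshold could mean a corrected p.** Section 11 does not say unadjusted, and section 12.2.3 refers to standard software for the imaging analyses. That reading is possible, but nothing in the documents supports it, and a corrected threshold cannot be applied without a defined family.
- **The tests are correlated.** Six of the 26 reuse the SRRS, and PANSS, BNSS and SNS overlap on negative symptoms. This stands: 74% is an upper figure for 26 tests, and 48% to 62% is plausible.
- **A false positive is not always a claim for lf-rTMS.** This also stands. In a two-sided comparison with placebo, half of the false positives favour lf-rTMS: 1 − 0.975^26 = 48%. If lf-rTMS ranks first among four exchangeable groups in a quarter of false omnibus results, the figure is 1 − 0.9875^26 = 28%. A reader might take 74% as the chance of a false claim for lf-rTMS; it is the chance of at least one significant result in any direction.
- **Hypothesis 1a says all measures.** Read literally, every measure would have to succeed, which does not inflate error. But section 11.4 states no such joint criterion.
- **Adjusting clinical secondaries is partly a matter of preference** in a proof-of-principle trial with one primary endpoint. Agreed. The imaging correction and the exploratory labelling carry the point, not any particular ordered list.

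The count could also be larger. Testing each measure at each visit gives 43 tests without imaging and function (89% under independence), but section 11.4.3 can equally be read as one repeated measures analysis per measure.

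**Conclusion.** The point holds. A .05 rule is stated for all analyses, no control is stated for any family, and most hypotheses are not labelled exploratory. For 20 to 26 non-imaging tests, 1.0 to 1.3 false positives are expected. The chance of at least one is 64% to 74% under independence, or about 48% to 62% for 26 tests at correlation 0.5 to 0.3. These figures assume that all nulls are true and that each measure has one between-group test. Imaging raises them by an amount that cannot be fixed from the documents.

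Three stronger readings are not supported:

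- **That false positives are almost certain.** Under independence, 95% needs 59 null tests. A figure of 99% for connectivity alone needs something like 91 connections (14 bilateral regions, all pairs), which the plan does not state; section 11.1 names narrower targets, though partly as examples.
- **That these figures measure the risk for hypotheses 2a-2d.** Those hypotheses concern patient-control differences and baseline associations. Their nulls do not depend on whether rTMS works, and none of the 26 tests addresses them. They lack error control too, but this count does not size it.
- **That the primary result is inflated.** It is one ANOVA on one endpoint and keeps its own .05. The optional interim looks in section 11.4.4 are a separate matter.

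**What to change.** 1. Limit the .05 significance claim in section 11 to the primary SRRS test.
2. For imaging, predeclare the motor-network mask or the list of regions and connections, for example the targets already named in section 11.1 (thalamus-M1 connectivity, SMA and M1 task activity, SMA perfusion). Control family-wise error or FDR within each modality, for both the treatment-change analyses and the baseline patient-control and association analyses.
3. Report the remaining secondary tests with effect sizes and confidence intervals as exploratory. Alternatively, name a short list of week-3 key secondaries under Holm or a fixed order.
4. Align the all-measures wording of hypothesis 1a with that choice.

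The primary alpha and the 88 patients stay as they are. Fewer secondary and imaging results can be called significant. To illustrate why the list should be short: Bonferroni over 26 tests gives 0.05 / 26 = 0.0019 per test, and an effect of f = 0.23 under the section 11.2 assumptions would then have about 70% power instead of 96%. Because section 11 is protocol text, the change needs an amendment under section 2.10, with the ethics committee approval that section 2.3 requires for protocol changes.

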11.1 Hypotheses

Aim 1: investigate the clinical and functional neural changes following 15 sessions of daily rTMS

Hypothesis 1a (main hypothesis): lf-rTMS (inhibitory) will be superior over placebo or iTBS (facilitatory) in all clinical and motor behavioral measures, e.g. greater reduction in SRRS scores from baseline, greater increase in activity levels, or coin rotations.

Hypothesis 1b: lf-rTMS will reduce aberrant functional connectivity in the motor system, e.g. between thalamus and M1. lf-rTMS will alter regional CBF in the motor system and increase SMA and M1 activity during the fMRI task. No relevant changes are expected in the sham group, iTBS may deteriorate neural alterations.

Hypothesis 1c: cortical excitability will be differentially changed with rTMS. Lf-rTMS will increase SIC1, while iTBS will reduce SIC1.

Aim 2: characterization of psychomotor slowing (PS) in schizophrenia spectrum disorders compared to healthy controls

Hypothesis 2a: Patients will have poorer performance on all motor tasks, eg. reduced activity levels, increased postural sway, and less coin rotations

Hypothesis 2b: Patients will have aberrant structural and functional connectivity within the motor system, as well as increased CBF in basal ganglia and decreased CBF in premotor/motor cortex. Applying network metrics, the functional motor network will be less efficient in schizophrenia.

Hypothesis 2c: Behavioral measures of PS will be associated with aberrant motor network structure, perfusion, function, and connectivity. For example, patients with strong PS will have increased resting state functional connectivity between thalamus and M1. PS severity will be linked to reduced structural motor network efficiency, lower M1 and SMA activity during the fMRI task, and increased SMA perfusion at rest.

Hypothesis 2d: Patients will have increased motor cortex excitability (e.g. reduced SICI), which will be linked to measures of PS.

Aim 3 characterize short term dynamics of PS

Hypothesis 3a: in very few subjects we expect relevant spontaneous improvements in PS measures. The majority will have less than 20% fluctuation of motor parameters within 3 weeks

Hypothesis 3b: we expect slight longitudinal changes in resting state functional connectivity and perfusion of the motor system, but no structural changes.

Aim 4: to describe the short-term and medium-term clinical outcome of 3 weeks of rTMS intervention

Hypothesis 4a: patients receiving inhibitory rTMS will have better outcome (less PS, less general symptom severity) shortly after the intervention (at 6 week follow-up) compared to patients receiving placebo or facilitatory iTBS

Hypothesis 4b: patients receiving inhibitory rTMS will have better outcome (less PS, less general symptom severity) and superior function (social and global) at 6-month follow-up compared to patients receiving placebo or facilitatory iTBS

Hypothesis 4c (exploratory): changes in functional connectivity within the motor system from baseline to week 3 will predict better outcome at week 6, particularly reduced M1-thalamus functional connectivity.

11.2 Determination of Sample Size

The main effects of the 3-week interventions on PS (SRRS scores) will be calculated in a repeated measures design including 2 measures (Baseline, week 3) and four groups (If-rTMS, iTBS, sham, waiting group-If-rTMS). Assuming a moderate effect size ($f = 0.23$) as indicated by our pilot data in a repeated measures ANOVA with moderate correlation between time points (0.5), a power of 0.95 and an $\alpha = 0.05$, we would need 88 patients (22 per group).

11.3 Statistical criteria of termination of trial

No statistical stopping rules are planned.

11.4 Planned Analyses

11.4.1 Datasets to be analysed, analysis populations

All data from subjects in the intent-to-treat population, who received at least one dose of rTMS will be used in the analyses of rTMS effects. We will conduct sensitivity analyses in all trial-completers (see 11.5).

In the analyses on biological and clinical correlates of PS, we will use all data of the baseline assessment, thus including data from subjects who dropped-out prior to the first rTMS session.

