SUSAR	Suspected Unexpected Serious Adverse Reaction
TMF	Trial Master File
UPSA Brief	UCSD Performance-based Skills Assessment Brief version

STUDY SCHEDULE

Study Periods	Screening	Treatment, Intervention Period				Follow-up	
		1	2*	3	4	5	6
Visit	1	2*	3	4	5	6	7
Time (week)	-1	0	1	2	3	6	24
Patient Information and Informed Consent	x						
Demographics	x						
CASH and SCID (history)	x						
In- /Exclusion Criteria	x						
Physical Examination	x						
Pregnancy Test	x						
Psychopathology (TALD, NES)		x					
Randomisation		x					
Administer rTMS (5 sessions per week)		x	x	x			
Primary Variable SRRS		x	x	x	x	x	x
Motor scales UPDRS, BFCRS, AIMS, IPAQ		x			x	x	x
Psychopathology (PANSS, BNSS, SNS)		x			x	x	x
Actigraphy and coin rotation		x			x	x	x
Posturography		x			x		
TMS cortical excitability		x			x	x	x
Cerebral MRI		x			x		
Functional outcome (SOFAS, GAF, UPSA-brief)		x				x	x
Concomitant Therapy		x	x	x	x		
Adverse Events		x	x	x	x		

* please note that in the waiting group assessments of visit 2 will be repeated after 3 weeks and thereafter the protocol will be identical (see below).

Study protocol for patients in the waiting group

Study Periods	Screening	Treatment, Intervention Period					Follow-up	
		2	3	4	5	6	7	8
Visit	1	2	3	4	5	6	7	8
Time (week)	-1	0	3	4	5	6	9	24
Patient Information and Informed Consent	x							
Demographics	x							
CASH and SCID (history)	x							
In- /Exclusion Criteria	x							
Physical Examination	x							
Pregnancy Test	x							
Psychopathology (TALD, NES)		x						
Randomisation		x						
Administer rTMS (5 sessions per week)			x	x	x			
Primary Variable SRRS		x	x	x	x	x	x	x
Motor scales UPDRS, BFCRS, AIMS, IPAQ		x	x			x	x	x
Psychopathology (PANSS, BNSS, SNS)		x	x			x	x	x
Actigraphy and coin rotation		x	x			x	x	x
Posturography		x	x			x		
TMS cortical excitability		x	x			x	x	x
Cerebral MRI		x	x			x		
Functional outcome (SOFAS, GAF, UPSA-brief)		x	x				x	x
Concomitant Therapy		x	x	x	x	x		
Adverse Events			x	x	x	x		

Study protocol for control subjects

Study Periods	Screening	Observation period	
		2	3
Visit	1	2	3
Time (week)	-1	0	3
Proband Information and Informed Consent	x		
Demographics	x		
SCID	x		
In- /Exclusion Criteria	x		
Physical Examination	x		
Pregnancy Test	x		
Primary Variable SRRS		x	x
Motor scales UPDRS, BFCRS, AIMS, IPAQ		x	x
Actigraphy and coin rotation		x	x
Posturography		x	x
TMS cortical excitability		x	x
Cerebral MRI		x	x

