6. STUDY DESIGN

6.1 General study design and justification of design

The design of this single-site study is a 4 parallel-arm, double-blind, randomized, placebo-controlled trial. Patients will be randomized to one of four treatment arms. Patients will all receive TMS over the left SMA in 15 daily sessions over 3 weeks as add-on treatment. In three groups, assessments will be conducted immediately before and after the three weeks treatment (1 Hz, iTBS, and Placebo), while the fourth group will receive active treatment (1Hz) only after a 3 week waiting period with no additional intervention. After 6 months we will perform a clinical follow-up assessment. The interventions will be conducted by a small team (2 persons) who will know the stimulation parameters. All assessments will be conducted by a different team, who is completely blind to treatment and specifically trained to use the instruments and rating scales. Patients are also blind to treatment, because stimulation site is the same for all groups and there will be no change of protocols during the study. The placebo group will be stimulated with a placebo coil that looks identical and emits identical noises compared to the real TMS coil, but without any magnetic impulse emission. Assessments with clinical rating scales will be complemented by objective and instrumental motor tests that are not prone to rater bias. Therefore, both the patients and the assessors are blind to treatment protocol.

The study will include patients with schizophrenia spectrum disorders who currently have psychomotor slowing according to the SRRS. The protocol arms are chosen to test the clinical efficacy and neurophysiological changes of 15 sessions 1 Hz rTMS for psychomotor slowing in schizophrenia spectrum disorders. The placebo-arm is required to demonstrate an effect of rTMS as add-on treatment. The active control is required to demonstrate an opposite effect at the neural level compared to active treatment. Finally, the waiting list is important to characterize potential self-limitation of the condition under study. Because these subjects are referred to a waiting list, they will receive active treatment thereafter. This group will not be completely blinded, as they will know to be in the active treatment group from week 3 through week 6.

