7.4 Criteria for withdrawal / discontinuation of participants

Participants may discontinue the trial at any time or withdraw consent. Furthermore, the treating physicians may request study discontinuation in case of significant deterioration of the condition at any time during the intervention period. All data from subjects in the intent-to-treat population, who received at least one dose of rTMS will be further used in the analyses. We will apply the last-observation-carried-forward (LOCF) method in the final analyses. In case a patient withdraws consent before the first rTMS stimulation, we will recruit an additional patient. The number of all patients recruited and randomized will be reported in the publications. All data from neuroimaging acquisition and motor behaviour will be used whenever possible, e.g. for analyses of baseline associations between brain imaging and behavior. In case of withdrawal due to adverse events or serious adverse events there will be follow-up examinations after 14 days and repeatedly until the problem is resolved, see 9.2.5.

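### The at-least-one-dose rule has no exception for the waiting list, whose first dose comes after its week-3 SRRS, so week-3 completers who then decline rTMS fall outside the primary comparison

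*Combined protocol and SAP*

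**What the plan says.** Section 11.4.1 restricts the set to intent-to-treat patients "who received at least one dose of rTMS will be used in the analyses of rTMS effects". Section 7.4 applies the same condition without limiting it to rTMS effects: patients "who received at least one dose of rTMS will be further used in the analyses". Section 11.4.1 relaxes it only for the baseline correlates of psychomotor slowing, "thus including data from subjects who dropped-out prior to the first rTMS session".

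The primary analysis (11.4.2) names no other set. Its ANOVA has two time points within "subjects: baseline and week 3) and four groups", one of them the waiting group. Section 11.2 describes the same test as addressing "The main effects of the 3-week interventions on PS (SRRS scores").

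On timing, section 6.1 describes three arms assessed immediately before and after treatment, "while the fourth group will receive active treatment (1Hz) only after a 3 week waiting period with no additional intervention". The Study Schedule footnote adds: "please note that in the waiting group assessments of visit 2 will be repeated after 3 weeks and thereafter the protocol will be identical". The visit list in 9.1.2 puts the waiting arm's week-3 SRRS and its first five sessions under one visit, and 8.2.2 confines its rTMS to weeks 3 to 6.

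Three other provisions bear on the point. Sections 7.4 and 11.5 recruit an additional patient when consent is withdrawn before the first stimulation. Section 11.5 plans LOCF, with a completer sensitivity analysis. Section 8.5 has the data of withdrawn participants analysed and stored in coded form like everyone else's.

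**The concern.** An at-least-one-dose rule does little harm when the first dose closely follows randomisation in every arm. Here that is true of three arms only. In the waiting arm, membership of the set is settled after the outcome has been rated, so it can depend on that outcome. A patient whose slowing lifts unaided may see no reason to begin 15 sessions; one who worsens may also leave.

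The comparisons at stake are the four-group omnibus test and the comparison of SRRS change between waiting list and placebo, which the synopsis lists as an outcome. The purpose of the arm is touched too: section 6.1 says "the waiting list is important to characterize potential self-limitation of the condition under study", and Hypothesis 3a expects few spontaneous improvers. If the wider wording of 7.4 governs that aim, improvers who decline rTMS would go uncounted.

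**Working it through.** **1. The plan's own figure.** Section 11.2 gives f = 0.23, correlation 0.5, alpha 0.05, power 0.95, four groups and two measures. For the group-by-time interaction, λ = f²·N·m/(1−ρ) = 0.23² × 88 × 2 / 0.5 = 18.62 on 3 and 84 df, so power is 0.957. The smallest N is 86, or 88 in four equal groups, so the stated 88 reproduces. Losing 5 waiting-list patients (N = 83, f held fixed) still leaves power of 0.944. The issue is selection, not power.

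**2. Order of events.**

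| | Groups 1-3 | Waiting list |
|---|---|---|
| Baseline SRRS | week 0 | week 0 |
| First rTMS session | straight after baseline | after the week-3 assessments |
| Week-3 SRRS | after the sessions | before the first session |
| Entry to dosed set settled | before the week-3 outcome | after the week-3 outcome |

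**3. Two kinds of undosed waiting-list patient.** (a) Those who leave before week 3 have no week-3 SRRS; they are ordinary missing data under any definition of the set. (b) Those who give a week-3 SRRS and then decline rTMS are excluded by the wording alone. Each patient of type (b) moves the arm mean by d/22, for example 1.0/22 = 0.045 SD.

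**4. Size.** The documents give no drop-out rate, so these inputs are assumptions: p = undosed share of the waiting arm, d = their difference in mean change (in SD), s = share of the undosed who have a week-3 SRRS.

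- Under the rule: shift = p·d, whatever s is. For 10% and 0.5 SD: 0.10 × 0.5 = 0.05 SD. For 20% and 1.0 SD: 0.20 × 1.0 = 0.20 SD.
- With every week-3 SRRS used: residual = d[p − ps/(1 − p + ps)]. For 20%, 1.0 SD and s = 50%: 0.20 − 0.10/0.90 = 0.09 SD.

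Type I error was simulated with no true difference, 22 per arm, extra patients not recruited, and the corresponding patients in groups 1-3 fully observed. Ranges span two scalings: SD of 1 within leavers and stayers, or SD of 1 overall.

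| Case | Shift | Omnibus type I error |
|---|---|---|
| 10%, 0.5 SD, rule as written | 0.05 SD | about 5.2% |
| 20%, 1.0 SD, rule as written | 0.20 SD | about 7.5-8% |
| Same, corrected set, s = 0 | 0.20 SD | unchanged |
| Same, corrected set, s = 50% | 0.09 SD | about 5.6% |
| Same, corrected set, s = 100% | 0 | about 5% |

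A different selection model, removing 4 of 22 waiting-list patients with a propensity correlated r with improvement, gave about 5% at r = 0, 7.2% at r = 0.5 and 15.9% at the extreme r = 1.

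**5. LOCF in the corrected set.** The waiting arm has no SRRS between weeks 0 and 3, so LOCF there means zero change. Take 20%, 1.0 SD and s = 50%. The unobserved share is 0.20 × 0.50 = 0.10, and leavers differ from the arm mean μ by (1 − 0.20) × 1.0 = 0.8 SD. The error is 0.10 × |μ ± 0.8|:

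| True mean improvement μ | Leavers improve more | Leavers improve less |
|---|---|---|
| 0 | 0.08 SD | 0.08 SD |
| 0.4 SD | 0.12 SD | 0.04 SD |
| 0.8 SD | 0.16 SD | 0.00 SD |

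Observed values alone give about 0.09 SD throughout. Neither method is better in general.

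**The case against.** The strongest reply is that the plan does not clearly exclude these patients. Section 8.5 has withdrawn patients' data analysed, and the clause on additional patients in 7.4 and 11.5 does not say that the earlier patient's data are discarded. This stands in part: the exclusion comes only from the dose rule, and the text contradicts itself. It does not remove the problem, because 8.5 names no analysis set. A narrower reading, that analyses of rTMS effects leave out the waiting list, would leave one of the four arms in the primary test with no defined set.

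A second reply is that most of the simulated inflation could be ordinary missing data. That is right, and it is why the results are split by s. Since the week-3 rating and first sessions fall under one visit, the interval in which a completer can decline looks short. Care is mostly inpatient or dayclinic (3.7) and active treatment is promised, so losses may be few.

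A third reply is that the simulation gives leavers in groups 1-3 their true week-3 values, whereas the plan uses LOCF. If those patients also stop early and LOCF keeps none, one third or two thirds of their change, omnibus error at 20% and 1.0 SD was 5.0-6.7% in five of six cases and 8.8% in one. The 7.5-8% figure therefore assumes that such patients would have stayed in groups 1-3.

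Neither LOCF nor the completer analysis answers the point: LOCF cannot help a patient outside the set, and completers are a narrower set still.

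**Conclusion.** The concern holds in a limited form. The dose rule, applied literally, makes the waiting arm's entry into a week-3 comparison depend on something that happens after week 3, and it conflicts with 8.5. Under the stated assumptions the effect runs from negligible (about 5.2% at 10% and 0.5 SD) to about 7.5-8% (at 20% and 1.0 SD). Only the part due to week-3 completers who decline rTMS is caused by the wording. If loss is unrelated to change, there is no bias.

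Three stronger conclusions might be inferred, and the documents do not support them:

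- That the main hypothesis is compromised. lf-rTMS versus sham and versus iTBS compare arms that all qualify at session 1, so this asymmetry does not touch them.
- That the plan discards these patients' data outright. Section 8.5 points the other way; the passages conflict.
- That LOCF must be abandoned in the waiting arm. Its error can be larger or smaller than that of observed values, depending on which patients leave.

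**What to change.** In 7.4, 11.4.1 and 11.5:

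- Define the week-3 primary set as all randomised patients with a baseline SRRS, analysed as randomised in all four arms, whether or not rTMS was later received.
- Use every week-3 SRRS obtained, including from waiting-list patients who then decline rTMS.
- Keep randomised patients in the set when an additional patient is recruited; recruitment restores the count, not the randomised comparison.
- Reconcile 8.5 with this set.
- Keep the at-least-one-dose set as a sensitivity analysis of the three immediately stimulated arms.
- Apply one missing-data rule to all arms, and add a sensitivity analysis of the zero-change assumption that LOCF makes in the waiting arm, for example observed values or a mixed model in all arms.

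The cost is a little wording and analysis work, with no new patients or visits. Under LOCF, undosed patients with only a baseline SRRS will enter as zero change. Bias from patients who leave before week 3 without a rating remains.
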